For reporting purposes, all relevant oral corticosteroid entries will be standardized by converting to a prednisone equivalent dose, and will be reported under the term 'Prednisone'. A listing of all compounds reported as prednisone will be produced along with the conversion factor applied.

The study management team will monitor oral corticosteroids on an ongoing basis for data quality and to ensure all dose adjustments are being correctly captured. All efforts

Rituximab—F. Hoffmann-La Roche Ltd
20/Statistical Analysis Plan WA29330

will be made to resolve missing or ambiguous data prior to database lock. In the case that data queries cannot be resolved, data will be handled in a conservative manner as described in the sections below.

The intervals for each dose of oral corticosteroid captured during the taper are expected to be continuous and non-overlapping. Patients who are adequately controlled by their blinded treatment may discontinue oral corticosteroids altogether, but may re-start treatment as required to treat any increases in disease activity. With this in mind, the use of available data will be maximized and incorporated into the imputation of missing or partial dates as follows:

Missing Term	Imputation Method
Start Date	
Missing Day	Latest of the following: Previous End Date+1 First day of the month
Missing Month	Previous End Date+1
Missing Year	No imputation
End Date	
Missing Day	Earliest of the following: Next Start Date-1 Last day of the month
Missing Month	Next Start Date-1
Missing Year	No imputation

Within two consecutive dosing intervals, if the end date of the first dose interval is missing and the start date of the second dose interval is missing, a midpoint approach using the start date of the first interval and the end date of the second interval will be used to assign a cut-off end date, providing these dates are available.

A missing or 'ongoing' final end date will be imputed with the exposure date. A missing initial start date will be imputed with Day 1 providing the end date is after Day 1, otherwise no imputation will be made.

If the total daily dose is missing then the dose will be imputed using the dose from the previous dose or the next dose, whichever is higher.

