Appendix 11 Imputation Rules for Partial or Missing Dates

	Start Date/Time	End Date/Time
Concomitant Medications	
Partially Missing Day: First day of the month (i.e., 01) Month: January Year: No imputation Seconds: 00 Minutes: 00 Hours: 00 Completely Missing Date: No imputation Time: 00:00:00 Note: if end time is available and start/end dates are equal and the imputed start time is after end time then impute start time with end time
	
Partially Missing Day: Last day of the month Month: December Year: No imputation Seconds: 59 Minutes: 59 Hours: 23 Completely Missing Date: No imputation Time: 23:59:59

Medical History	
Partially Missing Day: First day of the month (i.e., 01) Month: January Year: No imputation Seconds: 00 Minutes: 00 Hours: 00 Completely Missing Date: No imputation Time: 00:00:00 Note: if end time is available and start/end dates are equal and the imputed start time is after end time then impute start time with end time
	
Partially Missing Day: Last day of the month Month: December Year: No imputation Seconds: 00 Minutes: 00 Hours: 00 Completely Missing Date: No imputation Time: 00:00:00

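### The missing-month rule for oral steroid dates discards the recorded year, so it can fill a known off-steroid gap that crosses a year-end

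*SAP*

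**What the plan says.** SAP 4.7.2.1 relies on queries first and imputes only what remains: "In the case that data queries cannot be resolved, data will be handled in a conservative manner". It expects intervals without dosing, because controlled patients "may discontinue oral corticosteroids altogether, but may re-start treatment as required to treat any increases in disease activity". It then states its principle: "With this in mind, the use of available data will be maximized and incorporated into the imputation of missing or partial dates as follows". The table that follows has three levels:

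- **Day missing.** The start is the later of the day after the previous end and "First day of the month". The end is the earlier of the day before the next start and the last day of the month. The recorded month is used.
- **Month missing.** The start is "Previous End Date+1" and the end is "Next Start Date-1". The recorded year is not used.
- **Year missing.** Nothing is imputed.

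Because a missing year has its own row, the missing-month row covers records whose year is known.

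SAP 4.7.1.3 sends the steroid component of the primary endpoint to this same section. SAP 4.7.1.1 requires a PDAI activity score of 0 and prednisone at 0 mg/day for at least 16 consecutive weeks. Cumulative oral steroid dose is the first ranked secondary endpoint (SAP 4.7). Appendix 11 keeps the recorded year for other medications ("Day: First day of the month (i.e., 01) Month: January"), but SAP 4.10.4 exempts oral corticosteroids from it.

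**The concern.** The missing-month row discards information that the section has just undertaken to use, and it does so where that information matters. In an unbroken taper the rule is harmless, because the previous interval's end and the next start lie next to each other. When the neighbouring interval is a spell at 0 mg/day, the rule stretches a dose across the whole spell, including days that the recorded year shows were off steroids.

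Two derived quantities are exposed. The 0 mg/day run needed for sustained complete remission can disappear, and the cumulative dose can gain milligrams that the patient cannot have taken at that time.

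**Working it through.** **1. Design figure.** The imputation rule carries no figure of its own. The plan's related figure is about 80% power with 61 per arm, 65% versus 40%, two-sided 5% (SAP 2.3). Power = Φ{[|p1−p2|√n − 1.96√(2p̄(1−p̄))] / √(p1(1−p1)+p2(1−p2))} = Φ{[0.25√61 − 1.96√0.49875] / √0.4675} = 79.7%, which agrees.

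**2. Taper total, for scale** (Protocol Table 1). From the 60 mg start: 60×7 + 40×7 + 14×(30+20+15+12.5+10+7.5+5+2.5) = 2,135 mg over 18 weeks. From the 80 mg start, add 80×7 = 560 mg, giving 2,695 mg over 19 weeks.

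**3. Re-start month missing, gap crosses a year-end** (dates assumed). The last dose ends on 30 June 2017. A re-start at 20 mg, the protocol's own re-start figure (Protocol 3.1.2), is recorded only as 2018.

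- Rule as written: start = 1 July 2017, a year the record excludes.
- False days before 2018: 31+31+30+31+30+31 = 184. False dose: 184×20 = 3,680 mg, or 172% of 2,135 mg.
- Days at 0 mg kept in the gap: none.
- With a year bound: start = 1 January 2018 and 184 days at 0 mg are kept, against the 112 required.

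**4. End month missing on the last 2.5 mg step.** The gap is filled in the same way, but the false dose is modest: 112×2.5 = 280 mg for a 16-week gap and 203×2.5 = 508 mg for Week 19 to 48.

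**5. What a year bound recovers.** For a 20 mg re-start, averaged over 365 consecutive Day 1 dates (gap weeks assumed):

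| Gap (weeks) | Imputed date contradicts recorded year | 16-week run restored | Mean false dose, as written → bounded |
|---|---|---|---|
| 19–35 | 31% | 0.3% | 2,240 → 1,893 mg |
| 19–44 | 48% | 18% | 3,500 → 2,656 mg |
| 19–48 | 56% | 25% | 4,060 → 2,925 mg |
| 24–44 | 38% | 8% | 2,800 → 2,259 mg |
| 24–48 | 46% | 16% | 3,360 → 2,582 mg |

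A gap that lies within one calendar year is filled just as before.

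**6. Effect on the two tests.** One patient is 1/61 = 1.6 percentage points of an arm. If one or two rituximab responders were lost and no MMF responder, the formula in step 1 gives 73.9% or 67.4% power. A lost MMF responder would instead widen the observed difference. For cumulative dose, the default Wilcoxon Mann-Whitney test has SD(U) = √(61×61×123/12) ≈ 195. Moving one patient from the middle to the top shifts U by about 30, or 0.16 SD; the most extreme move is 61/195 = 0.31 SD.

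**The case against.** The trigger is narrow. Prednisone dose is assessed at every scheduled visit and captured on the eCRF (Protocol Appendix 1), and visits after Week 26 are at most 8 weeks apart. The SAP also provides for ongoing review and queries. A re-start known only to the year would have to survive all of that. This stands: the frequency may well be zero.

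The example in step 3 is favourable to the concern. An 18-week taper ending on 30 June 2017 puts Day 1 no later than 25 February 2017 and Day 364 no later than 23 February 2018, so the re-start must fall in the last 8 weeks of treatment. This stands too, and the table in step 5 shows more typical results.

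The rule can be defended as deliberately conservative, like the choice of the higher neighbouring dose when a dose is missing. That answers only part of the point. The overlap rule in the same section also assumes the higher dose for longest, but only within the dates provided. The missing-month row goes outside them.

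Three stronger readings are tempting, and the documents do not support them:

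- **The rule favours rituximab because more MMF patients re-start.** No figure for re-starts by arm is given. On the primary endpoint the rule penalises patients who are off steroids, and the design assumes more of these on rituximab (65% versus 40%), so the effect could run the other way.
- **The false milligrams distort the first ranked secondary.** Under the default rank test one patient matters little, as step 6 shows. A t-test is used only if the data prove normal.
- **Appendix 11 has the same fault for rescue drugs.** It keeps the recorded year. An imputed 1 January could precede Day 1, but no section says that the point of rescue is taken from an Appendix 11 date.

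**Conclusion.** The missing-month rows are wrong as written. Where an off-steroid gap crosses a year-end, they can impute a date that the record rules out, contrary to the section's own principle and to its missing-day rows. For an affected patient the known days at 0 mg/day in that gap are lost. Sustained complete remission is lost only if the gap held the sole qualifying run with PDAI activity at 0. The false dose can exceed a full taper when a 20 mg re-start is back-dated (3,680 mg against 2,135 or 2,695 mg), but is only a few hundred milligrams when the end month of the 2.5 mg step is missing.

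For the trial as a whole this is minor. The count of such records is not documented; 0 to 2 patients is an assumption, and the direction between arms is unknown. The power figures in step 6 are a one-sided worst case and should not be read as an expected loss. A reader might also infer that a year bound cures the problem. It does not: over the assumed gaps it restores a 16-week run in 0.3% to 25% of Day 1 dates.

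**What to change.** In the missing-month rows of SAP 4.7.2.1, use:

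- start = latest of (previous end date + 1, 1 January of the recorded year);
- end = earliest of (next start date − 1, 31 December of the recorded year).

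Because a gap within one calendar year would still be filled, list every oral steroid record with a missing month, by arm. If there are any, repeat the primary endpoint and cumulative dose as a sensitivity analysis, dating the stop or re-start from the visit-level prednisone assessments.

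The follow-up SAP reports the Week 52 analyses as complete (Section 1), so for those data the step is the listing and, if needed, the sensitivity check. Its Section 3.7.1.1 points back to the same handling rules, so the corrected wording should apply there too.

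For rescue medications under Appendix 11, at most state that an imputed start consistent with the recorded year may not precede Day 1. The adverse-event rule already takes the later of 1 January and first treatment when the month is missing. Do not set a floor at Day 84: the rescue criterion for treatment failure in SAP 4.2 has no Week 12 limit, so a floor could keep post-rescue data in analyses meant to stop at rescue.

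The cost is a small programming change and one listing; no new data are needed.

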4.7.2.2 Total Number of Flares

The total number of flares occurring during the treatment period will be evaluated by taking into account the number of flares experienced and the exposure period. Patient level flare and exposure data will then be aggregated, and the rate of flares compared between the RTX and MMF treatment groups. Rate of flare will be analyzed using a Poisson regression model with a log link and the log of each patient's duration in study as an offset variable. The model will include factors for treatment, region, duration of illness, baseline PDAI activity score, and baseline prednisone dose. The total number of flares, total exposure (weeks), and rate of flare will be presented by treatment group along with maximum likelihood estimates for the rate ratio, 95% confidence interval for the rate ratio, and p-value. A Pearson Chi-Square test will be used to assess over-dispersion of Poisson model. If an over-dispersion is detected based on this test, then a negative binomial model will be used. If the number of flares has an excess of zero counts according to the score test ([van den Broek, 1995](#)), a zero-inflated negative binomial model will be applied.

The exposure period for a patient will be the duration from Day 1 to the earliest of the following: early withdrawal, receipt of rescue, Week 52 visit.

Additional exploratory work may be undertaken to investigate the potential changes of flare rates over time, for example by assessing the number of flares over specified time intervals.

4.7.2.3 Time to Start of Sustained Complete Remission

Time to sustained complete remission is defined as:

date of first sustained complete remission response - date of first dose + 1

The date of first sustained complete remission is the first date at which a patient meets both criteria below, providing it was maintained for a minimum of 16 consecutive weeks:

- PDAI total activity score = 0
- Prednisone (or equivalent) dose = 0 mg/day

Data will be censored as follows:

- Patients withdrawing early from the study without achieving sustained complete remission will be censored at the time of study withdrawal.
- Patients meeting the criteria for treatment failure who have not achieved sustained complete remission prior to treatment failure will be censored at the Week 52 visit.
- Patients completing the 52-week treatment period who have not achieved sustained complete remission will be censored at the Week 52 visit.

Time to first sustained complete remission will be summarized using Kaplan-Meier curves along with the median, 95% confidence interval for the median, 25th and 75th

Rituximab—F. Hoffmann-La Roche Ltd
22/Statistical Analysis Plan WA29330

percentiles for each treatment group if available. The log-log transformation will be used to compute the 95% confidence intervals.

A stratified log-rank test will be used to test the time to first sustained complete remission between the RTX and MMF treatment arms over the 52-week treatment period, adjusting for the stratification factors used at randomization. A sensitivity analysis may be carried out using the Wilcoxon test. The Wilcoxon test is expected to be more sensitive when the log-rank assumptions do not hold (e.g., convergence of the Kaplan-Meier curves).

The time to first sustained complete remission will be converted to weeks for the presentation of Kaplan-Meier curves and all associated statistics. The Proc Lifetest procedure in SAS will be used to generate the Kaplan-Meier curves and hypothesis testing.

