All patients who withdraw from the treatment period or who complete the total 52-week treatment period must return for post-*Week 52* SFU assessments at 12, 24, 36, and 48 weeks after either the early withdrawal visit or study treatment completion, respectively. Thus, patients will be followed for approximately 1 year in the SFU period. A schedule of assessments during the SFU period is provided in [Appendix 2](#).

Before Week 12, patients who experience treatment failure (as defined in Section [3.1.3](#)) will require an early withdrawal visit and will be followed in the SFU period to receive standard-of-care treatment per the investigator's best medical judgment.

From Week 12 through Week 52, patients who experience treatment failure (as defined in Section [3.1.3](#)) are eligible to receive rescue therapy during the treatment period with another immunosuppressive medication, IV Ig, plasmapheresis, or another treatment or procedure as per the investigator's best medical judgment. An early withdrawal visit is not required for a patient to receive rescue therapy, and patients should continue to be followed in the study per the 52-week treatment period (see [Appendix 1](#)).

If a patient receives rescue therapy with rituximab, the number and timing of infusions will be at the discretion of the investigator. Every effort will be made to maintain the study blind, but the patient may be unblinded at the discretion of the Principal Investigator's safety assessment. Patients who receive rescue infusions with rituximab from Week 12 through Week 24 will not receive the scheduled rituximab or matching placebo infusions on Days 168 and 182. Careful consideration should also be given as to whether MMF/matching placebo are continued following rescue therapy with any immunosuppressive medication.

Evaluation of the primary endpoint will occur at Week 52. To prevent potential unblinding due to observed efficacy or laboratory changes, a dual-assessor approach will be used to evaluate efficacy and safety.

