3.1.3 Definition of Treatment Failure

Treatment failure is the occurrence of any one of the following events:

- After disease control has been achieved, a two-step increase in prednisone (or equivalent) dose to ≥ 20 mg/day for more than 2 weeks to treat increased disease activity during the corticosteroid taper
- Failure to achieve disease control after receiving 240 mg/day PO prednisone (or equivalent) for 1 week

Disease control is defined as the time at which new lesions cease to form and established lesions begin to heal (beginning of the consolidation phase).

- Increase in MMF/matching placebo dosage above 2 g/day
- Initiation of any rescue therapy (addition of another immunosuppressive medication, additional rituximab open-label doses, IV Ig, plasmapheresis, or another treatment or procedure) as determined by the investigator's best medical judgment

Patients experiencing treatment failure prior to achieving sustained complete remission will be categorized as non-responders in the primary analysis, but will continue to be followed in the study per the schedule of assessments. Patients who achieve sustained complete remission without experiencing an event constituting treatment failure beforehand will not be categorized as non-responders, regardless of whether they subsequently meet the criteria during the remaining treatment period.

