2.3 DETERMINATION OF SAMPLE SIZE

The primary efficacy endpoint of this study is the proportion of patients (excluding TM patients) achieving a sustained complete remission, as assessed at Week 52, that has been maintained for ≥ 16 consecutive weeks during the 52-week treatment period. With use of limited data available in the literature from randomized clinical trials of MMF and investigator-initiated trials of rituximab ([Beissert et al. 2010](#)), it is estimated that approximately 40% of patients with PV receiving MMF will achieve a sustained complete remission. It is estimated that patients receiving rituximab will induce a sustained complete remission rate of 65%. On the basis of these assumptions, a total of 122 patients randomized to either the rituximab arm or the MMF arm in a 1:1 ratio (61 patients in the rituximab arm and 61 patients in the MMF arm) will yield approximately 80% power in a two-sided test at the 5% significance level. To account for the 10 TM patients excluded from the primary efficacy analysis, approximately 132 patients will be randomized in total. The sample size calculation was performed using nQuery Advisor 7 using the two-group chi-squared test of equal proportions. The primary analysis method using a Cochran-Mantel-Haenszel test adjusting for stratification factors is expected to provide at least 80% power to detect the difference in proportions.

Rituximab—F. Hoffmann-La Roche Ltd
8/Statistical Analysis Plan WA29330

No adjustment will be made for dropouts. Patients withdrawing early from the study or meeting the criteria for treatment failure (including rescue therapy) will be assessed based on available data up until the point of withdrawal or treatment failure only for the primary endpoint. Patients with missing or incomplete data where a status cannot be determined after applying relevant imputation rules will be set to non-responders.

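### SAP 4.7.2.3 gives a patient who fails treatment and also leaves the treatment period two censoring dates, with no rule on which one governs

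*SAP*

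**What the plan says.** SAP 4.7.2.3 lists three censoring rules for patients without an event.

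- Withdrawal: "Patients withdrawing early from the study without achieving sustained complete remission will be censored at the time of study withdrawal".
- Treatment failure: patients "who have not achieved sustained complete remission prior to treatment failure will be censored at the Week 52 visit".
- Completers without sustained remission are censored at the Week 52 visit.

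The arms are then compared with a stratified log-rank test. SAP 4.7 places this endpoint third in a fixed sequence of five. Once a p-value is not below 0.05, nothing later in the sequence can be declared significant.

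Protocol 3.1.1 says that patients who fail before Week 12 "will require an early withdrawal visit and will be followed in the SFU period". Footnote a of the SAP schedule of assessments (Appendix 3) agrees. Protocol 3.1.3 says of failures in general that they are non-responders "but will continue to be followed in the study per the schedule of assessments".

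SAP 4.5 cuts each patient's data at the earlier of the Week 52 visit and early withdrawal. It substitutes Day 365 for a missing Week 52 visit, but only for patients who complete the treatment period.

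**The concern.** A failure before Week 12 is a treatment failure and, by protocol, also an early withdrawal. The first rule dates that patient's censoring in the first 12 weeks and the second dates it at Week 52. Section 4.7.2.3 does not say which applies. The second rule also names a visit that the patient will not have, and the Day 365 substitute does not reach this group. Two programmers could both follow the text and obtain different p-values for a type-I-controlled endpoint.

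The choice matters because of timing. The event needs a prednisone dose of 0 mg/day, and the taper guideline does not reach that for about 18 weeks. A patient censored before then is in no risk set when events begin, so known failures drop out of the comparison rather than counting as patients who did not remit. If one arm has more early failures, its remission curve is raised relative to the other. That can cost power or produce a false difference. A miss here also closes off time to flare and change in DLQI.

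**Working it through.** **Inputs from the documents.** SAP 2.3 assumes 40% sustained remission on MMF and 65% on rituximab, 61 patients per arm, and a two-sided 5% level. SAP 4.7.2.3 requires a 16-week run. Step lengths come from the taper guideline (Protocol Table 1, SAP Appendix 4). No failure or dropout rate is given, so all loss rates below are assumptions.

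**The plan's own figure.** SAP 2.3 says that 122 patients "will yield approximately 80% power in a two-sided test at the 5% significance level" for the primary comparison. With a pooled proportion of 0.525:

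z = (0.25 × √61 − 1.96 × √(2 × 0.525 × 0.475)) / √(0.40 × 0.60 + 0.65 × 0.35) = (1.953 − 1.384) / 0.684 = 0.83

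Power is 79.7%, so the figure is reproduced. No power is stated for time to remission.

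**When events can start.** From 60 mg (Step 2), Steps 2 and 3 take 1 week each and Steps 4 to 11 take 2 weeks each: 1 + 1 + 8 × 2 = 18 weeks. From 80 mg it is 19. The latest start that allows a 16-week run is 52 − 16 = Week 36. The guideline permits departures, so Week 18 is approximate.

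**Effect on the Kaplan-Meier estimate.** If a fraction p of an arm remits and a fraction d fails and is censored before the first event, the Week 52 estimate is p/(1 − d) under the withdrawal rule and p under the failure rule. Other withdrawals are ignored here.

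| Early failure, MMF / rituximab | True remission, MMF / rituximab | Estimate under withdrawal rule | Difference (rituximab − MMF) |
|---|---|---|---|
| 15% / 3% | 40% / 65% | 0.40/0.85 = 47.1%; 0.65/0.97 = 67.0% | 19.9 points, against a true 25 |
| 15% / 3% | 50% / 50% | 0.50/0.85 = 58.8%; 0.50/0.97 = 51.5% | −7.3 points, against a true 0 |
| 5% / 3% | 40% / 65% | 0.40/0.95 = 42.1%; 0.65/0.97 = 67.0% | 24.9 points, against a true 25 |

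**Effect on the test.** Log-rank simulation with 61 per arm, early failure of 15% (MMF) and 3% (rituximab), and a further 5% of each arm withdrawing without failure:

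| Censoring | Power, 65% vs 40% | Rejection, equal remission |
|---|---|---|
| Failures at withdrawal | about 54% | about 13% |
| Failures at Week 52, other leavers at withdrawal | about 77% | about 5% |
| Everyone without remission at Week 52 | about 76% | about 5% |

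With early failure of 5% against 3%, the first two rows differ in power by about 1 point. A repeat of 2,000 trials per scenario (four random strata, early failures at Weeks 3 to 12, other withdrawals at Weeks 4 to 40, equal remission set at 50%) gave 52%, 78% and 76% for power and 11%, 5% and 6% for equal remission. The gap at 5% against 3% was 2 points.

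**The case against.** **The overlap may be only apparent.** The withdrawal rule speaks of leaving the study. Safety follow-up is one of the study's three periods, and Appendix 3 calls the visit a treatment withdrawal visit. On that reading an early failure has left treatment but not the study, and only the failure rule applies. The SAP's own usage undercuts this. Section 2.4 sets the primary analysis for when all patients have reached Week 52 or withdrawn early from the study, and an early failure now in safety follow-up fits only the second description. Section 4.5 likewise cuts data at early withdrawal.

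**The intent seems clear.** The failure rule is the more specific one. Section 4.7.1.1 uses whichever of failure and withdrawal comes first, and 4.7.1.5 lets failure govern for a patient who later withdraws. This stands as a guide to intent, and it favours the failure rule. Those sections concern the primary endpoint, however, and supply neither a precedence for 4.7.2.3 nor a date.

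**Broader readings.** A reader might infer that every early leaver has two dates. That is not so: a leaver without treatment failure has one, the withdrawal date. A reader might also infer that censoring at withdrawal always inflates remission in the arm that loses more patients. For leavers without failure, that requires that they would not have remitted, which the documents do not establish. If they would have remitted like those who stayed, such censoring is not biased. In simulation, equal loss of 10% per arm left rejection under equal remission near 5%.

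**Carrying every leaver to Week 52.** A reader might think this necessary because the primary analysis treats such patients as non-responders. It is a different estimand, and in the scenario above it gains nothing once the failure rule governs (76% against 77%). Censoring ordinary withdrawals at withdrawal is conventional, and time to flare (4.7.2.4) does the same.

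**Conclusion.** The conflict is real but confined to patients who meet treatment failure and also leave the treatment period: every failure before Week 12, by protocol, and any later failure who withdraws. For them the plan gives two dates, no order between the two, and no Week 52 visit on which to apply the second.

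The size depends on how far early failure differs between arms, which the documents do not say. At an assumed 15% on MMF and 3% on rituximab, the choice moves power between about 54% and 77%, and rejection under equal remission between about 13% and 5%. At 5% against 3% it hardly matters. In the first case the distortion works against rituximab. With more early failure on rituximab it would work in its favour. These figures rest on assumed loss rates and remission times, and on the taper guideline being followed closely enough that few remissions start before Week 18. That early failures count as patients without remission is not an added assumption: SAP 4.2 classes failure before remission as non-response.

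The documents do not support a general finding of bias from censoring at withdrawal.

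**What to change.** In SAP 4.7.2.3:

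1. State that the treatment-failure rule takes precedence over the withdrawal rule for any patient who meets both.
2. State that the censoring date for such a patient is study Day 365 when there is no Week 52 visit.
3. Keep censoring at withdrawal for leavers without treatment failure.
4. Add a sensitivity analysis that carries all patients without sustained remission to Day 365, matching the primary endpoint's non-responder convention.

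The cost is a few sentences of SAP wording and one extra run. Nothing changes in patient management or data collection.
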